8.5.1.2 Multiplicity

Since no interim analyses are to be performed and the primary efficacy analysis consists of a single treatment comparison on one endpoint, no multiplicity adjustments will be made.

8.5.1.3 Multicenter Studies

Center effects will be explored as detailed in the SAP.

8.5.2 Primary Analysis of Efficacy

The primary efficacy analysis is the LDOCF SBM count at Week 1. SBM is defined as any BM that does not occur within 24 hours after rescue medication use.

For the primary efficacy variable of observed Week 1 SBM count, the 90% CIs of the treatment ratio between the sprinkle and capsule formulations will be calculated and the equivalence of the two medications can be claimed if the equivalence limits are within the interval of [0.8, 1.25].

The primary efficacy analysis will be performed in PP population.

8.5.3 Secondary Endpoints

8.5.3.1 Superiority Analysis of Observed SBM Count at Week 1 for Lubiprostone Sprinkle and Lubiprostone Capsule vs. Matching Placebo

The observed SBM count will be summarized by treatment group. ANCOVA for the observed SBM count with baseline SBM count as a covariate and the van Elteren test stratified by baseline SBM frequency rate (< 1.5 or ≥ 1.5) and pooled sites will be performed for the following comparisons:

- The sprinkle formulation of lubiprostone vs. the placebo group
- The capsule formulation of lubiprostone vs. the placebo group

8.5.3.2 Change from Baseline in Observed SBM Count at Week 1

Changes from baseline in observed SBM count will be summarized by treatment group. The 90% CIs of the treatment ratio between the sprinkle and capsule formulations will be calculated. ANCOVA for the change from baseline in observed SBM count and the van Elteren test stratified by baseline SBM frequency rate (< 1.5 or ≥ 1.5) and pooled sites will be performed for the following comparisons:

- The sprinkle formulation of lubiprostone vs. the placebo group
- The capsule formulation of lubiprostone vs. the placebo group

8.5.3.3 Overall and Mean Change from Baseline in Constipation Signs and Symptoms at Week 1

Overall and mean changes from baseline at Week 1 will be summarized based on subject reported data as to the degree of:

- Straining associated with SBMs; and
- Stool consistency of SBM.

The following rating scales will be used:

Stool consistency: Bristol Stool Form Scale (7-point scale);

Bowel straining: 0=Absent, 1=Mild, 2=Moderate, 3=Severe, 4=Very severe.

The overall mean scores, as well as changes from baseline, for the 7-day treatment will be calculated for each subject. The mean scores will be summarized using descriptive statistics for each treatment group. The 90% CIs of the treatment ratio between the sprinkle and capsule formulations will be calculated. ANCOVA and the van Elteren test will be performed to detect differences from baseline between the sprinkle and capsule formulations of lubiprostone and the matching placebo group.

8.5.3.4 SBM Frequency Rate at Week 1

SBM frequency rate at week 1 will be summarized by treatment group. The 90% CIs of the treatment ratio between the sprinkle and capsule formulations will be calculated. ANCOVA, using Week 1 SBM frequency rate as the dependent variable will be used to compare treatment groups with baseline SBM frequency rate as a covariate. The van Elteren test stratified baseline SBM frequency rate (< 1.5 or ≥ 1.5) and pooled sites will be performed to detect differences from baseline for lubiprostone sprinkle and lubiprostone capsule vs. matching placebo.

In order to adjust for early withdrawals or missing days, subjects with less than 7 days of treatment will have the Week 1 SBM frequency rates adjusted as follows:

$$7 \times \text{Number of SBMs} / (\text{Number of days treated}).$$

If the number of observed days is less than 4 days, then the data will be considered insufficient and the rate will be missing for that subject. No imputation will be performed for missing data.

8.5.3.5 Mean Change from Baseline in SBM Frequency Rate at Week 1

Changes from baseline in SBM frequency rate at week 1 will be summarized by treatment group. The 90% CIs of the treatment ratio between the sprinkle and capsule formulations will be calculated. ANCOVA for the change from baseline in observed SBM count and the van Elteren test stratified by baseline SBM frequency rate (< 1.5 or ≥ 1.5) and pooled sites will be performed for the following comparisons:

- The sprinkle formulation of lubiprostone vs. the placebo group
- The capsule formulation of lubiprostone vs. the placebo group

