8.1 Determination of Sample Size

This is a phase 3, multicentre, double-blinded, randomized, placebo-controlled study evaluating the bioequivalence of Sprinkle and Capsule formulations of lubiprostone when administered orally in subjects with chronic idiopathic constipation. Subjects will be randomized (1:1:1 ratio) to receive either lubiprostone sprinkle, lubiprostone capsule or matching placebo BID in a blinded, double-dummy fashion.

In clinical studies of the lubiprostone capsule formulation during the CIC development program, the average observed SBM count at Week 1 for lubiprostone 24 mcg BID was 5.62 with a standard deviation of 4.24. In order to achieve the conclusion of equivalence between the sprinkle and capsule formulations of lubiprostone, the 90% confidence interval for the ratio of means has to be contained within the interval of [0.8, 1.25]. Thus, a sample size of 156 per group is required to achieve 90% power at a 10% significance level.

Assuming 10% of subjects do not meet criteria for inclusion in the Per Protocol population and/or do not have observed week 1 SBM count due to early withdrawal or other reasons, 174 subjects per treatment group (a total of 522 subjects) will be required for this study.

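### Sprinkle/capsule ratio intervals are prescribed for change-from-baseline and ordinal symptom endpoints, where the ratio depends on the baseline level, on a possibly small denominator, or on the coding origin

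*Combined protocol and SAP*

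**What the plan says.** Section 8.5.3.2 reads: "Changes from baseline in observed SBM count will be summarized by treatment group. The 90% CIs of the treatment ratio" between sprinkle and capsule will be calculated. The same sentence, "The 90% CIs of the treatment ratio between the sprinkle and capsule formulations will be calculated", appears in three other places:

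- section 8.5.3.3, in the paragraph on overall mean scores and changes from baseline for straining and stool consistency;
- section 8.5.3.4, for SBM frequency rate;
- section 8.5.3.5, for change in SBM frequency rate.

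Stool consistency uses the 7-point Bristol scale, whose lowest category is Type 1 (Appendix 3). Straining is coded "Bowel straining: 0=Absent, 1=Mild, 2=Moderate, 3=Severe, 4=Very severe".

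No method for the ratio interval is named, and nothing is said about negative or near-zero means. Section 8.5.3.3 does not say whether the ratio is of overall means, of changes, or of both. In 8.5.3.2, 8.5.3.3 and 8.5.3.5 the ANCOVA and van Elteren tests compare each formulation with placebo. The ratio is therefore the only sprinkle-versus-capsule estimate specified there. Equivalence limits of 0.8 and 1.25 are attached only to the primary Week 1 SBM count (sections 8.1 and 8.5.2).

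**The concern.** A ratio of means suits a count or rate, where zero means none. It does not carry over well to the other endpoints, for three separate reasons.

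- Subtracting baseline from both arms moves the ratio away from 1, although nothing about the formulations has changed.
- A mean change that is small against its SD makes the denominator unstable. The interval can become very wide or lose a finite limit, and a log-scale method fails altogether on negative changes.
- A mean score on a scale without a zero gives a ratio that depends on the number assigned to the first category.

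Comparing sprinkle with capsule is the purpose of the trial, and these are its supporting estimates. As written, they could be misleading or uninterpretable, and the ratio method might be chosen only after the data are seen.

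**Working it through.** **Inputs from section 8.1.** "the average observed SBM count at Week 1 for lubiprostone 24 mcg BID was 5.62 with a standard deviation of 4.24"; and "a sample size of 156 per group is required to achieve 90% power at a 10% significance level". Inclusion criterion 7 caps baseline below 3 SBMs per week. The documents do not give the baseline mean, the SD of the change in count, or the mean and SD of the symptom changes. Values used for these are assumptions and are marked as such.

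**The plan's own figure.** CV = 4.24/5.62 = 0.754, and the log-scale SD = sqrt(ln(1 + 0.754²)) = 0.671. Then n = 2 × 0.671² × (1.282 + 1.645)² / (ln 1.25)² = 155, and exact power at 156 is 90.1%. So 156 reproduces with 10% per one-sided test; whether that matches a 90% interval is a separate question. With 10% loss, 156/0.9 = 173.3, hence 174. The plan gives no figure for the secondary ratio intervals.

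**(a) Change in SBM count or rate: location.** With capsule mean 5.62 and common baseline b, a count ratio of 0.90 puts sprinkle at 5.058. The change ratio is (5.058 - b)/(5.62 - b):

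- b = 0.5: 4.558/5.12 = 0.89
- b = 1.5: 3.558/4.12 = 0.86
- b = 2.5: 2.558/3.12 = 0.82

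**(a) Change in SBM count: width.** Take identical arms with equal observed means m, SD s, n = 156 per arm and t = 1.650 (310 df). The 90% Fieller limits are (1 ± sqrt(2g - g²))/(1 - g), with g = t²s²/(n m²). The SD of the change is assumed to equal the Week 1 SD, 4.24.

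| Endpoint | m | g | 90% interval |
|---|---|---|---|
| Week 1 count | 5.62 | 0.0099 | 0.87-1.15 |
| Change, b = 0.5 | 5.12 | 0.0120 | 0.86-1.17 |
| Change, b = 1.5 | 4.12 | 0.0185 | 0.82-1.21 |
| Change, b = 2.5 | 3.12 | 0.0322 | 0.77-1.29 |

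The difference interval is ±1.650 × 4.24 × sqrt(2/156) = ±0.79 SBM at every baseline.

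**(b) Change in straining or stool score.** Same formula, assumed SD 1.0, identical arms:

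- mean change -0.5: g = 0.070, interval 0.68-1.47
- mean change -0.3: g = 0.194, interval 0.51-1.97

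The interval is unbounded once g reaches 1, that is, once SD/|mean change| reaches sqrt(156)/1.650 = 7.6. The difference interval is ±1.650 × 1.0 × sqrt(2/156) = ±0.19 points in both cases.

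**(c) Overall mean stool score.** Illustrative means of 3.4 and 4.0 coded 1-7 give 3.4/4.0 = 0.85. Coded 0-6, the same answers give 2.4/3.0 = 0.80. This does not extend to change scores, because adding a constant to every code cancels in the change.

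**The case against.** The strongest reply is that these intervals are descriptive. The secondary sections attach no limits, decision rule or equivalence claim to them. A reader might infer that the secondary intervals will be judged against 0.8 and 1.25, so that the sprinkle could pass on count and fail on change. The documents do not support that: the limits belong to the primary count alone. This part of the reply stands and confines the harm to supportive estimates.

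It is also tempting to call all these intervals very wide. For change in SBM count that is not so: with the plan's mean and SD, the expected change lies well away from zero and the widening is moderate. Very wide intervals arise only for symptom change scores, and only if the mean change is small against its SD, on which the documents are silent. The coding argument applies to overall mean scores, chiefly Bristol. Straining has a labelled zero, and ratios of change are unaffected by shifting the codes.

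A ratio of mean changes can also be read as the share of the capsule's improvement that the sprinkle retains. That is a definable quantity, so it would be too strong to say it has no meaning. It still depends on baseline level, and it still needs a stated method when the denominator may be small. Section 8 leaves further detail to an SAP to be finalised before unblinding, so the gap can be closed there; the text as it stands does not close it.

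**Conclusion.** The point holds for sections 8.5.3.2, 8.5.3.3 and 8.5.3.5, as a defect in supportive estimation. It does not threaten the primary equivalence conclusion.

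Its size differs by endpoint. It is moderate for change in SBM count and, by the same argument, change in rate. It is potentially severe for straining and stool change scores. For overall mean Bristol scores the result depends on an arbitrary choice of coding.

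These sizes rest on 156 per arm, assumed baselines of 0.5 to 2.5 per week, the Week 1 SD carried over to the change in count, an assumed SD of 1.0 for symptom changes, and illustrative stool means. Lower baselines shrink the effect; at 0.5 per week it is slight. That the ratio depends on baseline and on coding origin needs none of these values.

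**What to change.** Keep the 90% ratio interval for SBM count and SBM frequency rate (8.5.3.4). In 8.5.3.2, 8.5.3.3 and 8.5.3.5, replace it with the sprinkle-minus-capsule difference in adjusted means and its 90% interval. Obtain this by adding that contrast, with the endpoint's baseline value as covariate, to the ANCOVA models now specified only against placebo; those three sections name no covariate at present. The ANCOVA sentence in 8.5.3.5 names change in SBM count as the response and should name the frequency rate. In 8.5.3.3, say that the contrast is reported for both the overall mean and the change.

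The cost is wording in the protocol or SAP before unblinding and one added contrast per endpoint. No new data, visits or subjects are needed. The downside is that the difference interval is also only descriptive, since no margin is set for these endpoints; the text should say so.

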2.2.1.2 Secondary Efficacy Endpoints

- Superiority analysis of observed SBM count at Week 1 for lubiprostone sprinkle and lubiprostone capsule vs. matching placebo
- Change from baseline in observed SBM count at Week 1
- Overall and mean change from baseline in stool consistency associated with SBMs at Week 1
- Overall and mean change from baseline in straining associated with SBMs at Week 1
- SBM frequency rate at Week 1
- Mean change from baseline in SBM frequency rate at Week 1

Details regarding BMs (time of occurrence and associated subject ratings of consistency and straining), as well as details regarding study medication and rescue medication administration (see [Appendix 3](#)), will be reported by subjects from Screening through the end of double-blinded treatment.

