4. SELECTION AND WITHDRAWAL OF SUBJECTS

4.1 Inclusion Criteria

Subjects must satisfy the following criteria before entering the study:

1. Subject is male or female, ≥ 18 years of age.
2. Subject either has medically-confirmed diagnosis of chronic constipation (per Rome III; [Appendix 1](#)), or meets the diagnosis as confirmed using the Rome III constipation module questionnaire ([Appendix 2](#)) during the Screening period.
3. Subject is able to comprehend and willing to sign an ICD approved by the IRB after explanation of the nature and objectives of the study and prior to the conduct of any study specific procedure.
4. If subject is taking concomitant medication (prescribed or over-the-counter) that affects gastrointestinal motility, he/she must discontinue use at the time of the Screening Visit (Visit 1) through the Follow-up Visit (Visit 4); these medications include:
 - a. Cholinesterase inhibitors; anti-spasmodic, anti-diarrheal, anti-constipation, or prokinetic agents; laxative agents (e.g., PEG 3350), including homeopathic remedies;
 - b. Tricyclic antidepressants; and/or
 - c. Any medication, at the discretion of the Investigator, known to relieve or cause constipation or constipation-related symptoms, and which the Investigator, based on the medical history of the subject, suspects to be a contributing factor to the patient's chronic constipation, or may otherwise confound the evaluation of treatment response.

Exceptions: Treatment with anticholinergic agents, SSRIs, SNRIs, or MAO inhibitors is allowed if a stable dose has been used for at least 30 days prior to the Screening Visit and not likely to change during the study.

5. If subject is taking a fiber supplement or a concomitant medication for the indication of lowering blood pressure, usage must have been at a stable dose and schedule for at least 30 days prior to the Screening Visit and not likely to change during the study.
6. Subject daily diary is at least 70% compliant for evening/end-of-day assessments during the Screening period.
7. Subject daily diary indicates an average of less than 3 spontaneous bowel movements (SBMs) per week during the 14 days prior to randomization.
8. Subject daily diary indicates one or more of the following for at least 25% of SBMs during the 14 days prior to randomization:
 - Bristol Stool Scale Type 1 or 2;
 - Moderate to very severe straining associated with SBMs; and/or
 - Sensation of incomplete evacuation.

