Note: For subjects with no reported SBMs during the Screening Period, it is not necessary to meet criteria for bowel movement characteristics, i.e., moderate to severe straining and straining at defecation.

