8.5.1.1 Missing Data

Only observed SBM count will be adjusted for missing data, and the missing data imputation will be performed using the following four methods:

Last Daily Observation Carried Forward (LDOCF): Subjects with any missing daily observed SBM count during the treatment week will have their daily value(s) imputed by carrying over the previous non-missing post-baseline SBM observed count, and the LDOCF method will be used for the primary efficacy analysis.

Average Daily Baseline Observation Carried Forward (BOCF): Subjects with any missing daily observed SBM count during the treatment week will have their daily value(s) imputed by the Baseline SBM observed count divided by 7.

Observed Case (OC) Analysis: All observed SBMs that occurred during Week 1 for each subject will be counted, without any missing data imputation being performed.

Regression Imputation: Subjects with missing Week 1 observed SBM count will have their value imputed using the regression equation found from regressing the Week 1 observed SBM count as the dependent variable for all subjects in the same treatment group on their baseline observed SBM count as the independent variable.

Median Imputation: The median observed SBM count for all subjects in the same treatment group will replace missing observed SBM count at Week 1.

BOCF, OC Analysis, Regression Imputation, and Median Imputation will be used as sensitivity assessments of the primary efficacy endpoint.

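### Section 8.5.3.3 tests stool consistency and straining as differences from baseline, so subjects admitted with no screening SBM drop out of those tests even when they have Week 1 scores

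*Combined protocol and SAP*

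**What the plan says.** Inclusion criterion 7 (section 4.1) sets an upper limit only: "Subject daily diary indicates an average of less than 3 spontaneous bowel movements (SBMs) per week during the 14 days prior to randomization". Zero therefore qualifies, and the note to criterion 8 provides for it: "For subjects with no reported SBMs during the Screening Period, it is not necessary to meet criteria for bowel movement characteristics".

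The symptom endpoints are tied to SBMs. Section 2.2.1.2 lists "Overall and mean change from baseline in stool consistency associated with SBMs at Week 1", with a parallel endpoint for straining. Section 8.5.3.3 names two ratings in the same terms, one of them given as "Stool consistency of SBM" and the other being the straining score, likewise restricted to SBMs. In Appendix 3 the diary asks for both ratings once per bowel movement, so a subject with no bowel movement gives no rating.

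Section 8.5.3.3 then says: "The overall mean scores, as well as changes from baseline, for the 7-day treatment will be calculated for each subject". The inferential test is set out as follows: "ANCOVA and the van Elteren test will be performed to detect differences from baseline between the sprinkle and capsule formulations of lubiprostone". That sentence goes on to name placebo as the comparator. Section 8.5.1.1 closes off imputation: "Only observed SBM count will be adjusted for missing data". The mITT and PP definitions in section 8.2 do not require an SBM, and the sensitivity analysis in section 8.5.4 concerns the primary endpoint only.

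**The concern.** A change from baseline needs a score at both ends. The plan admits subjects who lack the first, promises a change for every subject, and has no rule for those in whom it cannot be formed. Such subjects count as members of the analysis population but contribute nothing to the symptom tests against placebo. They are the entrants with the fewest SBMs, and many will have Week 1 ratings that go unused.

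A second group has no SBM in Week 1 and so no symptom score of any kind. That state arises after randomization and can depend on treatment, so the symptom comparison with placebo is made among subjects who had at least one SBM rather than among all those randomized. The plan does not say so.

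**Working it through.** **Who has which score**

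| SBM in screening | SBM in Week 1 | Week 1 mean score | Change from baseline |
|---|---|---|---|
| yes | yes | exists | exists |
| none | yes | exists | cannot be formed |
| yes | none | does not exist | cannot be formed |
| none | none | does not exist | cannot be formed |

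The second row is lost only because the test is on change. The last two rows are lost from any analysis of the score.

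The documents give no figure for either group, so there is none to reproduce. The sizes below are illustrations.

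**No SBM in Week 1**

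Input from section 8.1: Week 1 SBM count on lubiprostone 24 mcg BID, mean 5.62, SD 4.24. Assumption: negative binomial counts.

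- Shape: k = mean² / (SD² − mean) = 5.62² / (4.24² − 5.62) = 31.58 / 12.36 = 2.56.
- Share with zero SBMs: P(0) = (1 + mean/k)^(−k).
- Active, mean 5.62: 5.1%, about 9 of 174. A Poisson with this mean gives 0.4%, but its variance contradicts the stated SD.
- Placebo, mean not in the documents, same k: 7.5% at 4.5 (13 of 174), 9.0% at 4.0, 11.0% at 3.5, 13.7% at 3.0, 17.5% at 2.5 (30 of 174). Holding the coefficient of variation constant instead gives 6.6% to 12.4% over the same means.
- Sprinkle against capsule, with the sprinkle mean at the lower equivalence limit: 0.8 × 5.62 = 4.50, P(0) = 7.5%. The gap is 7.5 − 5.1 = 2.4 points, about 4 of 174.

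**No SBM in screening**

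Assumptions: the baseline score uses the 14 screening days; the untruncated mean is 0.75 to 2.0 SBMs per week; entry requires fewer than 6 SBMs in 14 days (an average below 3 per week). The share is P(0) / P(fewer than 6).

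| Untruncated mean per week | Poisson | Negative binomial, k = 2.56 |
|---|---|---|
| 0.75 | 22% (117 of 522) | 31% (164) |
| 1.0 | 14% (72) | 24% (126) |
| 1.5 | 5% (28) | 16% (84) |
| 2.0 | 2% (12) | 12% (64) |

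The range is about 2% to 31%. The shape 2.56 comes from treated Week 1 counts and is only borrowed here. Heavier overdispersion (k = 1) would give 27% to 37% at means of 2.0 down to 1.0 per week.

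**Both together, one example**

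Take 10% with no baseline SBM, and 5% (active) and 15% (placebo) with no Week 1 SBM, treated as independent. A change score then exists for 174 × 0.90 × 0.95 = 149 active and 174 × 0.90 × 0.85 = 133 placebo subjects, before other dropout.

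**Why the Week 1 score can replace the change score**

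Write the Week 1 score as a + b × treatment + c × baseline. Subtracting baseline from both sides gives change = a + b × treatment + (c − 1) × baseline. The treatment effect b is the same. So, for subjects with both values and with baseline as a covariate, the two ANCOVAs give the same answer. The Week 1 form can also keep subjects with no baseline score, by setting that score to a constant and adding an indicator for its absence. The indicator is fixed before randomization, so adjusting for it is valid.

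**The case against.** Several points on the other side are sound.

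- A missing baseline score is determined before randomization. A reader might infer that losing these subjects biases the comparison between arms. It does not; the cost is precision and generalizability.
- A reader might infer that zero-SBM entrants vanish from these endpoints altogether. The endpoint covers the overall score as well as the change, so a subject with Week 1 SBMs still enters the descriptive Week 1 mean. Such a subject also stays in the sprinkle/capsule ratio if that is taken on overall scores, which section 8.5.3.3 does not specify.
- A reader might infer that dropping Week 1 zeros makes sprinkle and capsule look more alike than they are. The documents do not support this: the difference in loss is only about 2.4 percentage points even at a ratio of 0.8, and smaller if the formulations act alike.
- Having no SBM already counts as a poor result in the primary analysis and in the SBM count and frequency endpoints, where zero is a valid value.
- Giving Week 1 zeros the worst rank is not a free repair. In a simulated rank test with no straining effect, 174 per arm and an assumed placebo mean of 3.5, worst-ranking rejected about 16% to 17% of the time at the 5% level, against 4% to 5% with zeros dropped. It partly re-tests SBM count. On the Bristol scale, which runs from hard lumps to watery, there is no clear worst end.
- Section 8 defers detail to a SAP whose text is not among the documents. It may contain a rule.

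What remains is that the protocol admits these subjects, tests a quantity they cannot have, and states no rule for them.

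**Conclusion.** The point holds as an avoidable loss in two secondary endpoints and an unstated condition on how their results can be read. Subjects with no screening SBM leave the ANCOVA and van Elteren tests against placebo although many will have usable Week 1 scores. The size depends on unstated baseline counts (about 2% to 31% under the Poisson and negative binomial assumptions above).

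Separately, the symptom comparison with placebo is conditional on having a Week 1 SBM. About 5% on active and 7% to 17% on placebo would fall outside it, given the negative binomial form and assumed placebo means of 4.5 down to 2.5. That difference between arms can affect the placebo comparison; its effect on the symptom estimates cannot be sized from the documents. The sprinkle-capsule comparison is little affected, and the primary analysis of SBM count is untouched.

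**What to change.** In section 8.5.3.3, or in the SAP before unblinding:

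1. Make the Week 1 mean score the ANCOVA outcome, with the baseline score (set to a constant when absent) and a no-baseline-SBM indicator as covariates.
2. Run the van Elteren test on the Week 1 score.
3. Keep change from baseline as a descriptive summary for subjects with both values.
4. Report by arm, beside each symptom result, the number with no SBM at baseline and the number with none in Week 1. Describe the results as conditional on having a Week 1 SBM.
5. Optionally, for straining only, add a sensitivity analysis giving the worst rank to subjects with diary data but no Week 1 SBM, labelled as a composite with SBM frequency.

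If the SAP already has a rule, the protocol need only refer to it. The cost is wording and a little programming, with no new data. The van Elteren test on the Week 1 score gives up adjustment for the individual baseline symptom score. If it uses the baseline SBM frequency strata (<1.5 or ≥1.5) named for the other endpoints, subjects with no screening SBM all fall in the lower stratum and some adjustment remains.
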